- DLQI: It is a questionnaire containing 10 items to assess the impact of AD on quality of life (QOL) in the past week, and the scores range from 0 (no disease) to 30 (severe disease); the higher the score, the worse the quality of life. Refer to [Section 17.2, Appendix B](#). DLQI score will only be assessed among subjects ≥ 16 years, and it will be assessed once a week during the study period.
- POEM: It is a questionnaire composed of 7 items to assess disease symptoms on a scale of 0-4 (dryness, itching, flaking off, cracking, sleeplessness, bleeding and weeping or oozing); the scores range from 0 (no disease) to 28 (severe disease); the higher the score, the worse the quality of life. Refer to [Section 17.3, Appendix C](#). It will be assessed once a week during the study period.

2) Investigator's efficacy assessments (completed by the investigator):

- IGA: The Validated Investigator Global Assessment for AD (vIGA-AD™) Scale is a 5-point classification scale based on the overall appearance of the skin lesions at a specific time point (0=clear; 1=almost clear; 2=mild; 3=moderate; 4=severe). It should be noted that in order to be eligible for selection, the IGA score must be ≥ 3 . See [Section 17.4, Appendix D](#). Please also note that IGA-1 should not contain scales.
- EASI: The EASI scale quantifies the severity and extent of AD, as well as the severity of erythema, infiltration, excoriation and lichenification of the four anatomical regions—head and neck, trunk, upper extremities and lower extremities. The total EASI score ranges from 0 (lowest) to 72 (highest); the higher the score, the higher the severity of AD (more severe). It should be noted that in order to be eligible for selection, the EAS score must be ≥ 16 . See [Section 17.5, Appendix E](#).
- The “Rule of Nines” is used to estimate the maximum percentage of AD-affected BSA in each area: head and neck [9%], anterior trunk [18%], back [18%], upper limbs [18%], lower limbs [36%] and genitals [1%]. The number of palms of AD-affected skin in a body part can be used to determine the extent (%) of AD involvement in that body part. Regardless of the age of the subject, the area of the subject's entire palm (five fingers adducted together) is about 1% of the subject's

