7.1. Overall Statistical Consideration

In the statistical tabulations, screening number of subjects is the universal unique identifier of subjects in the study.

General rules of descriptive statistics: Quantitative variables are described by mean, standard deviation, median, minimum, maximum, Q1 and Q3. In terms of rounding, the numbers of decimal places of the minimum and maximum are consistent with that of original value, while those of mean, medium, Q1, and Q3 are 1 more than that of the original value, and that of standard deviation is 2 more than that of the original value. Categorical variables are described by number and percentage of each category. The number of subjects is rounded to integer and percentage is rounded to one decimal place. It is unnecessary to present a percentage when the count is 0.

General rules of inferential statistics: Two-sided test is adopted for all statistical tests (unless otherwise specified). $P < 0.05$ will be considered statistically significant (unless otherwise specified). P value is rounded to 4 decimal places. If $P < 0.0001$, it is presented as ' $< .0001$ '; if $P > 0.9999$, it is presented as ' $> .9999$ '.

For primary analysis, the baseline of efficacy analysis is defined as the last available value before randomization in Stage 1, and the baseline of safety analysis is defined as the last available value before the first dose in Stage 1.

For the analysis in Stage 2, one group of baselines is defined for efficacy analysis and two groups of baselines are defined for safety analysis. The baseline of efficacy analysis is defined as the last available value before randomization in Stage 1. The baseline of safety analysis in Group 1 is defined as the last available value before the first dose. The baseline of safety analysis in Group 2 is defined as the last available value before the first dose in Stage 2. Efficacy analysis will be performed using the baseline of Group 1. Safety analysis will be performed to analyze the changes from baseline in laboratory test, ECG and vital signs at each visit using the baseline of Group 1 and the baseline of Group 2, respectively.

Statistical analyses will be performed using SAS 9.4.

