7.4.3. Analysis of the primary efficacy endpoint and key secondary efficacy endpoints

Label of estimand	Description of estimand	Main estimator			Sensitivity/ Supplementary analysis
		Analysis sets	Rules for imputation	Model/method for the main analytical methods	
Estimand of primary endpoint	
The difference in efficacy in patients aged 12 years and older with moderate to severe AD and weighing > 40 kg between the CBP-201 300 mg Q2W group and placebo group.
 
A patient is considered as treatment success if the patient has an IGA score of 0-1 which is decreased by ≥ 2 points from baseline at W16.
 
A patient should be regarded as treatment failure if he/she uses prohibited drugs/treatments specified in the protocol for which the study treatment must be early terminated or other rescue therapy that has a major impact on the assessment of the primary endpoint due to poor response, or has premature discontinuation of treatment/EOT due to AEs.
	FAS1 (will include all subjects in RS1 who have received the study drug at least once).	
For subjects who experience intercurrent events, their visits after the intercurrent events will be handled in accordance with the strategies for managing intercurrent events listed in Table 7.4.2.
 
If the target variable is still missing after application of the strategies for managing intercurrent events, the multiple imputation (MI) method will be used to impute the missing data in the placebo group, and the J2R (jump to reference) method will be used to impute the missing data in the CBP- 201 group.
	
Differences in response rates between the treatment group and placebo group and their 95% confidence intervals will be analyzed using the Cochran-Mantel-Haenszel test stratified by baseline disease severity (IGA 3 or 4). The Type I error level for statistical significance of the difference in response rates between CBP-201 and placebo is set at 0.05 (two-sided test).
	
Sensitivity analysis 1: When the target variable is still missing after application of the strategy for managing intercurrent events, it will be classified as treatment failure.
 
Sensitivity analysis 2: When the target variable is still missing after application of the strategy for managing intercurrent events, tipping point analysis will be used for analysis.
 
Sensitivity analysis 3: For the subjects who are incorrectly stratified and randomized, the analysis will be performed using the stratification during randomization and the same method as the main estimand;
 
Supplementary analysis 1: The analysis will be performed using the same method as the main estimand based on the PPS1.
 
Supplementary analysis 2: The treatment policy strategy will be used for all intercurrent events; the FAS1 will be used,

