Estimand of key secondary endpoints	
The differences in the following measures in patients aged 12 years and older with moderate to severe AD and weighing ≥ 40 kg between the CBP-201 300mg Q2W group and the placebo group:
 
 • The proportion of subjects achieving EASI-75 at W16 • The proportion of subjects whose weekly average PP-NRS is decreased by ≥ 4 points from baseline at W16; • The proportion of subjects whose weekly average PP-NRS is decreased by ≥ 3 points from baseline at W16; 	FAS1 (will include all subjects in RS1 who have received the study drug at least once).	
For subjects who experience intercurrent events, their visits after the intercurrent events will be handled in accordance with the strategies for managing intercurrent events listed in Table 7.4.2.
 
If the target variable is still missing after application of the strategies for managing intercurrent events, the multiple imputation (MI) method will be used to impute the missing data in the placebo group, and the J2R (jump to reference)
	
For categorical variables, differences in response rates between the treatment group and placebo group and their 95% confidence intervals will be analyzed using the Cochran-Mantel-Haenszel test stratified by baseline disease severity (IGA 3 or 4).
 
For continuous variables, analysis will be performed using an MMRM model that will include treatment group, baseline disease severity (IGA 3 or 4), baseline value of the
	
Sensitivity analysis 1: When the target variable is still missing after application of the strategy for managing intercurrent events, categorical variables will be classified as treatment failure. Continuous variables should be imputed with WOCF.
 
Sensitivity analysis 2: For the subjects who are incorrectly stratified and randomized, the analysis will be performed using the stratification during randomization and the method the same as the main estimator;
 
Supplementary analysis 1: The analysis will be performed using the same method as the main estimand based on the PPS1.
 
Supplementary analysis 2: The treatment policy strategy will be used for all intercurrent events; the FAS1 will be used,

Label of estimand	Description of estimand	Main estimator			Sensitivity/ Supplementary analysis
		Analysis sets	Rules for imputation	Model/method for the main analytical methods	

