	
 Change and percentage change in the weekly average PP-NRS from baseline at W16; The proportion of subjects achieving EASI-90 at W16 
A patient should be regarded as treatment failure if he/she uses prohibited drugs/treatments specified in the protocol for which the study treatment must be early terminated or other rescue therapy that has a major impact on the assessment of the key secondary endpoints due to poor response, or has premature discontinuation of treatment/EOT due to AEs. In this case, continuous variables should be imputed with WOCF.
		method will be used to impute the missing data in the CBP- 201 group.	corresponding endpoint, visit, interaction of visit and treatment group, and the LSMEAN estimate values and their 95% confidence intervals will be summarized.	and the missing data will be subject to the imputation rules of the main estimator, that is, the multiple imputation method (MI) will be used to impute the missing data in the placebo group, and the J2R (jump to reference) method will be used to impute the missing data in the test group.

In the J2R (jump to reference) method, when the data of subjects of the active treatment group are missing, it is assumed that their statistical results are the same as those of the placebo group, that is, it is considered that the pharmacological action of the drug for the active treatment group is the same as that of the placebo group. PROC MI will be used for J2R imputation, and the missing data of the active treatment group will be imputed with the results obtained by posterior predictive distribution of the placebo group. Markov Chain Monte Carlo (MCMC) will be used to extend the data, and a regression method will be used to generate M datasets (M is set as 30 for the primary analysis and as 1000 for other cases in this study). The imputed variables should include: treatment group, stratification factor (severity of baseline disease), baseline value of corresponding endpoint and measurement at each visit. Random seed is the earliest date of the first dose to all subjects.

Table 5 Random Seeds of Multiple Imputation

Endpoints	Random Seeds
IGA	Minimum date of the first dose
EASI	Minimum date of the first dose + 1
PP-NRS	Minimum date of the first dose + 2
BSA	Minimum date of the first dose + 3
SCORAD	Minimum date of the first dose + 4
DLQI	Minimum date of the first dose + 5
POEM	Minimum date of the first dose + 6

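### Does listing both the severity stratum and baseline IGA make the imputation model for the primary endpoint unworkable?

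*SAP*

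**What the plan says.** Section 7.4.3 of the later SAP imputes missing placebo data by multiple imputation. In the CBP-201 arm it uses jump to reference: "the missing data of the active treatment group will be imputed with the results obtained by posterior predictive distribution of the placebo group". The variables in the model are treatment group, "stratification factor (severity of baseline disease), baseline value of corresponding endpoint and measurement at each visit". IGA has its own row in the table of random seeds (Table 5), so this list governs the primary endpoint.

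The stratum is moderate (IGA 3) or severe (IGA 4) disease at baseline (SAP 3.1). Protocol 6.2 gives a 0 to 4 scale and says that "in order to be eligible for selection, the IGA score must be" at least 3. SAP 7.1 states that "the baseline of efficacy analysis is defined as the last available value before randomization in Stage 1".

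The main test is a "Cochran-Mantel-Haenszel test stratified by baseline disease severity (IGA 3 or 4". For mis-stratified subjects the sensitivity analysis differs: "the analysis will be performed using the stratification during randomization and the same method as the main estimand". The key secondary endpoints have the matching entry, "the analysis will be performed using the stratification during randomization and the method the same as the main estimator". Continuous endpoints use an "MMRM model that will include treatment group, baseline disease severity (IGA 3 or 4), baseline value of the" endpoint, and SAP 7.4.4 extends this to change in IGA.

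SAP v1.0 has the same imputation list and the same definition of baseline. Its sensitivity analysis goes the other way: it uses corrected strata.

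**The concern.** In the later SAP the randomised stratum is the sensitivity analysis, so the main analysis reads as using actual baseline IGA. For an eligible subject that value is 3 or 4, which is exactly the severity factor. The IGA imputation model then contains the same column twice, and so does the mixed model for change in IGA. The covariance matrix of the listed variables is singular. One could conclude that the imputation behind the primary result cannot be fitted as written and that the programmer must make an undocumented choice.

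The source of the stratum adds to this. Inferred by contrast with the sensitivity analyses, it is actual baseline IGA in the later SAP and the randomised stratum in v1.0. Incorrect stratification is a listed cause of protocol deviations among the 255 subjects (SAP section 6), so the two sources are not identical in these data. If the choice mattered, the primary p-value would depend on something the plan leaves open.

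**Working it through.** **1. The plan's own figure.** Inputs from Protocol 12.3: 27% v 9%, 144 and 72 completers, two-sided 0.05. Pooled rate = (144×0.27 + 72×0.09)/216 = 0.21. Null SE = √[0.21×0.79×(1/144+1/72)] = 0.0588. Alternative SE = √[0.27×0.73/144 + 0.09×0.91/72] = 0.0501. Power = Φ[(0.18 − 1.96×0.0588)/0.0501] = 90.2%, against 90% stated. 216/0.85 = 254.1, rounded up to 255. The second claim (28.1% v 10.7%) gives 85.9%, against more than 85% stated. None of this involves the imputation list.

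**2. Effect of an exact duplicate.** Let s be the severity factor and b baseline IGA, with s = b. Then β₁s + β₂b = (β₁+β₂)b. Only the sum is identified, and predictions use only the sum. With 85 simulated placebo subjects and an intercept, s, b and one later visit, there are 4 columns of rank 3. Dropping s changes the fitted values by about 2e-15. With all earlier visits as predictors of W16, predictive mean, predictive variance, residual variance and residual degrees of freedom agree to 7e-14 with and without s. Residual degrees of freedom are 85 − 6 = 79 either way.

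**3. Was the list meant column for column?** Investigator assessments in Stage 1 fall at baseline, W2, W4, W8, W12 and W16 (Protocol Table 1.1). The full list for IGA is therefore treatment group, severity, baseline and five visits: 8 variables. In the placebo fit that jump to reference draws on, treatment group is constant, so the covariance matrix has rank 6. Removing the duplicate leaves 7 variables, still of rank 6. A literal reading fails even after the duplicate is removed, so the list has to be read as the information to use.

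**4. If the stratum is the one used at randomisation.** Severity and baseline IGA then differ only in mis-stratified subjects. The documents give no count, so k of 255 is assumed. The chance that none of them is in placebo is C(170,k)/C(255,k):

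| k | 1 | 3 | 5 | 13 |
|---|---|---|---|---|
| chance | 0.667 | 0.295 | 0.129 | 0.004 |

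In those cases step 2 applies. Otherwise the placebo fit has full rank. The variance inflation is about 22, 11, 5.6 and 3.0 for 1, 2, 4 and 8 mis-stratified placebo subjects of 85 (50% severe assumed). The terms are then close to collinear but distinct, and the model can be fitted.

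**5. Does the CMH stratum matter?** Simulated trials had 255 subjects, 2:1 in blocks of 6, complete data, and an assumed odds ratio of response of 0.4 for severe v moderate. There were 40,000 trials per row.

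| Rates | k | Verdict differs | Power, randomised stratum | Power, actual stratum |
|---|---|---|---|---|
| 27% v 9% | 3 | 0.33% | 95.5% | 95.5% |
| | 5 | 0.46% | 95.4% | 95.4% |
| | 13 | 0.71% | 95.4% | 95.4% |
| | 26 | 0.99% | 95.2% | 95.4% |
| 28.1% v 10.7% | 3 | 0.44% | 92.5% | 92.5% |
| | 5 | 0.64% | 92.4% | 92.5% |
| | 13 | 0.92% | 92.4% | 92.6% |
| | 26 | 1.27% | 92.3% | 92.7% |

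The last row differs by 0.4 as rounded. A repeat with 100,000 trials per row and 50% severe put the largest gap at 0.27 points. With 18% response in both arms, each choice rejects in 4.8% to 5.2% of trials. Power exceeds the plan's 90% because all 255 subjects have data here.

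**The case for a change.** The best case for a change is reproducibility. Section 7.4.3 should let a second programmer rebuild the primary imputation. For IGA it does not say which column to keep or which stratum to use, and the two SAP versions point in opposite directions on the second question. Naming the source once would cost a line of text and would make the stratum sensitivity analysis easier to read.

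Part of this stands. The source of the stratum is not named, and under the actual-baseline reading the duplication is real. The later SAP's front matter is not available and may record why the wording changed.

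The claimed consequence does not stand. A singular covariance matrix does not show that the procedure fails, and whichever of two identical columns is dropped, the imputed values have the same distribution. Nor would it be safe to delete the severity factor outright. If the stratum is the randomised one, the factor is a separate pre-specified covariate. SAP v1.0 may well have governed the primary analysis of the 255: it is dated one day after the blinded review of 19 September 2022 and was written mainly for Stage 1. Its sensitivity analysis on corrected strata reads most naturally as a contrast with a main analysis on randomised strata, and on that reading there is no exact duplicate in the model as a whole.

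**Conclusion.** No change follows. Listing baseline IGA once would alter no imputed-value distribution, estimate or p-value, so it brings no gain. The unnamed stratum source is a gap that analysts can fill sensibly: either choice is valid, both hold about 5% type I error, and the SAP already plans an analysis on the alternative. The size is a changed verdict in 0.3% to 1.3% of simulated trials and at most about 0.3 points of power, even with 26 of 255 subjects mis-stratified.

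This rests on assumed mis-stratification counts, an assumed odds ratio of 0.4 and complete-data simulations. The simulations therefore measure the choice of CMH stratum, not the imputation; for imputation the argument is the algebra of the exact duplicate. One case is left open. SAP section 6 lists subjects whose baseline severity did not meet the entry requirement. If any of them had baseline IGA below 3, severity and baseline IGA would differ for that subject, and a stratum would have to be assigned. The documents give neither the number nor the scale involved. EASI, PP-NRS and the other endpoints are unaffected by the duplication, because their baseline value is a different variable from the stratum. Change in IGA lies outside the tested sequence.

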7.4.4. Other efficacy endpoint analysis

The categorical efficacy endpoint analysis in Stage 1 will be performed using the same method as the primary efficacy endpoint analysis.

The continuous efficacy endpoint analysis in Stage 1 will be performed using the same method as the secondary efficacy endpoint analysis.

According to the investigator's judgment, AD aggravation or deterioration of symptoms which requires drugs or treatments originally prohibited by the protocol for rescue therapy will be defined as "AD recurrence" event.

The number of AD recurrence, the number of subjects with AD recurrence, and the number of days of AD recurrence in Stage 1, from baseline to W8, from W9 to W16 will be analyzed. The total number of AD recurrence in each stage will be summarized. AD recurrence will be summarized by the number of recurrences, that is, 0, 1, 2 and ≥ 3 . The number and percentage of subjects will be calculated. Chi-squared test will be adopted to compare whether the differences between the two groups are statistically significant. The total number of subjects with AD recurrence in each stage will be summarized, and the number and percentage of subjects will be calculated. Chi-squared test will be performed to compare whether the differences between the two groups are statistically significant. The number of days of AD recurrence in each stage will be summarized by descriptive statistics.

7.4.5. Efficacy analysis in stage 2

During efficacy analysis in Stage 2, the percentage of subjects achieving efficacy endpoint and its confidence interval will be calculated for categorical efficacy endpoints. For continuous efficacy endpoints, ANCOVA model will be used to calculate the mean, the Least Square Mean, 95% confidence interval and SE of the change from baseline and percentage change from baseline of each efficacy endpoint. The model will include treatment group, severity of baseline disease (IGA 3 or 4), and baseline value of corresponding endpoint. Inferential statistics will not be performed during the Stage 2 analysis. The following two analyses will be performed.

Analysis method 1: Categorical efficacy endpoints after the occurrence of events will be regarded as no response for subjects who have the following conditions; continuous efficacy endpoints after the occurrence of events will be imputed using WOCF in Stage 2; other missing data except for the conditions above will be imputed using multiple imputation (MI).

- Group adjustment

- Premature discontinuation of treatment/EOT due to AEs
- Use of prohibited drugs/treatments specified in the protocol as a rescue treatment for AD due to poor response, which has a major impact on the assessment of the efficacy endpoints, including:

The following prohibited drugs/treatments are used during Stage 2 (W16 to W52):

- Dupilumab or any anti-IL-4R α or IL-13 antibodies;
- Topical PDE-4 inhibitors or JAK inhibitors;
- Systemic treatment with corticosteroids or other immunosuppressive and/or immunomodulatory agents, such as cyclosporine, mycophenolate mofetil, azathioprine, methotrexate, or oral JAK inhibitors;
- Cell depletion agents (e.g., rituximab) or other biological agents;
- Other investigational drugs (non CBP-201) or treatments.

Or the following prohibited drugs/treatments are used for a cumulative period of more than 7 days during Stage 2 (W16 to W52):

- Initiation of SIT, or dose up-regulation;
- TCS or TCI (topical drugs can be used for AD lesion areas only);
- Phototherapy (NBUVB, UVB, UVA1, PUVA), sunbed or any other LED therapies;
- Bleaching baths more than 2 times a week;
- Any drug for the treatment of AD (If topical drugs, only those used for AD lesion areas will be counted) that may interfere with the evaluation of efficacy results or affect the evaluation of AD severity.

Analysis method 2: The analysis will be performed using the actual observed values. If the actual observed value is missing, it will be imputed by MI.

During MI in Stage 2, M data sets will be generated by regression method (M is set as 1000 during Stage 2 analysis).

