12.3. Basis of Sample Size

The sample size of 255 cases (in a 2:1 ratio, 170 cases in the CBP-201 300 mg Q2W group, and 85 cases in the placebo group. Assuming that the dropout rate in the treatment group is 15%, then about 144 cases in the CBP-201 300 mg Q2W group and 72 cases in the placebo group will be able to complete the study) can provide a power of 90% to detect the therapeutic effect on the primary endpoint in the CBP-201 300 mg Q2W group and the placebo group. This power is calculated based on the following assumption: the proportion of subjects reaching the primary efficacy endpoint is 27% in the CBP-201 300 mg Q2W group and 9% in the placebo group, and the significance level for two-sided tests is 0.05.

Based on the results of another conducted phase II international multicenter clinical study of CBP-201 in patients with moderate-to-severe atopic dermatitis, the proportion of subjects reaching the primary efficacy endpoint was 28.1% in the CBP-201 300mg Q2W group and 10.7% in the placebo group, at a two-sided test significance level of 0.05, and if the results of this trial are similar to that of the WW001 trial, the above sample size would provide a power of more than 85% to detect the therapeutic effect on the primary endpoint between the CBP-201 300 mg Q2W group and the placebo group. Therefore, no adjustment is made to the sample size.

The primary analysis of this study will still be based on the 255 subjects enrolled in accordance with V2.1 and its earlier versions of the protocol. Subjects newly enrolled (approximately 81 cases) based on the protocol after V2.1 will not be included in the primary analysis, and only supplementary analysis will be performed.

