 - Group D: The subjects will receive a subcutaneous injection of CBP-201 300 mg every 4 weeks. In order to maintain the injection every 2 weeks blind, when not receiving CBP-201, the subjects will receive an injection of placebo 2 ml once every 4 weeks until W50.
- Subjects who have not achieved EASI-50 in the W16 pre-administration treatment assessment will receive the following treatment starting from W16:
 - Group E: The subjects will receive a subcutaneous injection of CBP-201 300 mg every 2 weeks until W50.
- If subjects in group C and group D have not achieved EASI-50 in two continuous pre-administration treatment assessments, they will be assigned to group E to be treated with subcutaneous injection of CBP-201 300 mg every 2 weeks from the visit when EASI-50 is not achieved for the second time to W50.

Table 2: Dosing Regimen by Group in Stage 2

Group	W16	W18	W20	W22	W24	W50
Group C	2XC	2XC	2XC	2XC	2XC	2XC
Group D	2XC	2XP	2XC	2XP	2XC	2XP
Group E	2XC	2XC	2XC	2XC	2XC	2XC

Note: C=CBP-201; P=placebo; #X=number of ampoules.

All subjects (including the subjects who prematurely discontinue treatment) will be followed up for 8 weeks after the last dose.

The overall study design is shown in the diagram below:

[figure not shown]

Figure 1: Study Design Diagram

Note:

- 1: The subjects will receive a loading dose of the study drug (investigational product/placebo) on D1 at a dose of 600 mg (4 ml);
- 2: Response is defined as a 50% or greater decrease in the EASI score;
- 3: In order to maintain the injection every 2 weeks blind, when not receiving CBP-201, the subjects will receive an injection of placebo 2 ml once every 4 weeks until W50.
- 4: If subjects in group C and group D have not achieved EASI-50 in two continuous pre-administration treatment assessments, they will be assigned to group E to be treated with subcutaneous injection of CBP-201 300 mg every 2 weeks from the visit when EASI-50 is not achieved for the second time to W50.

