7.4.4. Other efficacy endpoint analysis

The categorical efficacy endpoint analysis will be performed using the same method as the primary efficacy endpoint analysis.

The continuous efficacy endpoint analysis will be performed using the same method as the secondary efficacy endpoint analysis.

According to the investigator's judgment, AD aggravation or deterioration of symptoms which requires drugs or treatments originally prohibited by the protocol for rescue therapy will be defined as "AD recurrence" event.

The number of AD recurrence, the number of subjects with AD recurrence, and the number of days of AD recurrence in Stage 1, from baseline to W8, from W8 to W16 will be analyzed. The total number of AD recurrence in each stage will be summarized. AD recurrence will be summarized by the number of recurrences, that is, 0, 1, 2 and ≥ 3 . The number and percentage of subjects will be calculated. Chi-squared test will be adopted to compare whether the differences between the two groups are statistically significant. The total number of subjects with AD recurrence in each stage will be summarized, and the number and percentage of subjects will be calculated. Chi-squared test will be performed to compare whether the differences between the two groups are statistically significant. The number of days of AD recurrence in each stage will be summarized by descriptive statistics.

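### The Stage 1 comparison of AD recurrence has no time-at-risk adjustment and no withdrawal rule, so it can be biased if withdrawal differs between arms

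*SAP*

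**What the plan says.** SAP 7.4.4 (later version) covers three quantities: the number of recurrences, the number of subjects with a recurrence, and the days of recurrence. Each is taken over Stage 1, baseline to W8, and W9 to W16.

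- Counts: "AD recurrence will be summarized by the number of recurrences, that is, 0, 1, 2" and three or more.
- Subjects: "The total number of subjects with AD recurrence in each stage will be summarized, and the number and percentage of subjects will be calculated".
- Test, for both of these: "Chi-squared test will be adopted to compare whether the differences between the two groups are statistically significant".
- Days: "The number of days of AD recurrence in each stage will be summarized by descriptive statistics".

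SAP version 1.0 has the same methods in its 7.4.4, with the second interval written as W8 to W16, as in protocol 9.5.1. Neither version gives an offset, a person-time denominator, a censoring rule, or a rule for subjects who leave before W8 or W16.

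The same section opens with a general sentence: "The categorical efficacy endpoint analysis in Stage 1 will be performed using the same method as the primary efficacy endpoint analysis". The recurrence paragraph then sets its own test.

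The formal comparison exists in Stage 1 only, because SAP 7.4.5 says "Inferential statistics will not be performed during the Stage 2 analysis".

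**The concern.** A count of events, or the percentage with any event, depends on how long each subject was watched. SAP 7.4.4 treats a subject seen for 3 weeks and a subject seen for 16 weeks as equally informative. If the first had no recurrence before withdrawing, the default is to place that subject in the zero row for all of Stage 1. For W9 to W16 the SAP does not say whether a subject who had gone before W9 stays in the denominator.

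If the arms lose observation time at different rates, part of the apparent treatment difference reflects follow-up and not recurrence. At stake are the Stage 1 recurrence comparisons with placebo. The primary and key secondary tests are not affected.

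**Working it through.** **Does another part of the SAP repair this?**

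- *Imputation.* SAP Table 5 lists random seeds for seven scales (IGA, EASI, PP-NRS, BSA, SCORAD, DLQI, POEM) and none for recurrence.
- *Intercurrent-event rules.* SAP 7.4.2 turns major rescue use for poor response into non-response. Need for rescue is what defines a recurrence, so that rule cannot sensibly govern this endpoint.
- *Time-adjusted rates.* SAP 7.5.2 plans annual incidence, but only for AEs in SS3. SAP Table 4 shows no placebo column for SS3.

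None of these repairs the comparison with placebo.

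**The plan's own dropout figure.** The documents state no figure for recurrence. Protocol 12.3 has "Assuming that the dropout rate in the treatment group is 15" per cent, with 170 and 85 randomised: 170 × 0.85 = 144.5 and 85 × 0.85 = 72.25. These match its completers of 144 and 72, so the 15% is applied equally to both arms.

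**Assumptions for the illustration.** True 16-week risk p is 40% on placebo and 15% on CBP-201, with a constant hazard. A fraction d leaves, uniformly over 16 weeks, with no observation afterwards. Everyone stays in the denominator.

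Full Stage 1, with L = −ln(1 − p):

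observed = (1 − d)·p + d·[1 − p/L]

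- Placebo: L = 0.5108, bracket = 0.2170.
- CBP-201: L = 0.1625, bracket = 0.0770.
- At d = 15%: placebo 0.85 × 0.40 + 0.15 × 0.2170 = 0.3725; CBP-201 0.85 × 0.15 + 0.15 × 0.0770 = 0.1391.

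Second half, with q = 1 − √(1 − p):

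observed = (1 − d)·q + d·0.5·[1 − q/(L/2)]

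- Placebo: q = 0.2254, bracket = 0.1175.
- CBP-201: q = 0.0780, bracket = 0.0396.
- At d = 15%: placebo 0.2004, CBP-201 0.0693.

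| Dropout, placebo / CBP-201 | Stage 1, % | Difference | Ratio | Second half, % | Difference | Ratio |
|---|---|---|---|---|---|---|
| none | 40.00 v 15.00 | 25.00 | 0.375 | 22.54 v 7.80 | 14.74 | 0.346 |
| 15 / 15 | 37.25 v 13.91 | 23.35 | 0.373 | 20.04 v 6.93 | 13.11 | 0.346 |
| 25 / 10 (assumed) | 35.42 v 14.27 | 21.15 | 0.403 | 18.37 v 7.22 | 11.15 | 0.393 |
| 10 / 25 (assumed) | 38.17 v 13.18 | 24.99 | 0.345 | 20.87 v 6.35 | 14.53 | 0.304 |

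Differences are taken before rounding. Relative losses in the difference:

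- 15 / 15: 1 − 23.35/25.00 = 7%; second half 1 − 13.11/14.74 = 11%.
- 25 / 10: 1 − 21.15/25.00 = 15%; second half 1 − 11.15/14.74 = 24%.

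True risks of 30% v 10% and 50% v 20% give similar relative losses.

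**Second model.** This uses risks of 30% v 15% and a constant dropout hazard.

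- 15 / 15: the difference falls from 15.0 to 13.9 points and power from 79% to 76%.
- 25 / 10: the difference falls to 12.0 points (20% lost) and power to 64%.
- 10 / 25: the difference is 15.5 points and the ratio 0.46 against a true 0.50.

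**Type I error.** No true effect, same dropout model, 200,000 simulated chi-squared tests with 85 and 170 subjects:

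- 15 / 15: about 5%.
- 25 / 10: 6.3% (true risk 30%) to 8.2% (true risk 50%).
- 30 / 10: 7.9% to 11.0%.

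**The case against.** The strongest reply is that the only dropout figure in the documents is equal by arm. There the ratio is almost unbiased and type I error stays near 5%. That stands. The larger losses rest on an unequal split that is assumed.

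The model also overstates lost time. SAP 3.1 says "All subjects (including the subjects who prematurely discontinue treatment) will be followed up for 8 weeks after the last dose", so a subject whose last dose is at W2 should be observed to about W10. Lost time comes mainly from withdrawal from the study, where protocol 7.3 asks for follow-up only as far as possible. This lowers the expected size but leaves the gap.

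PPS1 is a second analysis set for Stage 1 efficacy. It removes many early leavers (missed W12 and W14 doses, three missed doses, or no W16 IGA and EASI). But it selects on what happened after randomisation, so it supports the comparison without correcting it.

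The general sentence at the top of SAP 7.4.4 could be read as bringing in multiple imputation. The separate chi-squared test and the absent seed speak against that reading.

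A reader might infer four stronger points that the documents do not support:

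- *Every early leaver is scored recurrence-free.* A recurrence before leaving is counted. Under protocol 8.2.2 systemic rescue stops study drug, so some discontinuations follow a counted recurrence.
- *Subjects gone before W9 are fixed in the W9 to W16 denominator.* The SAP is silent on this.
- *The treatment difference is distorted.* That depends on withdrawal by arm, which the documents do not give.
- *More withdrawal on CBP-201 overstates the effect.* On the difference scale it hardly does (24.99 v 25.00 points). It holds for the ratio (0.345 v 0.375).

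**Conclusion.** The gap is real and should be closed, but its effect is conditional. SAP 7.4.4 compares recurrence without time at risk or a withdrawal rule, and nothing else in the SAP repairs the placebo comparison.

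At the protocol's equal 15% dropout the harm is mild: a loss of about 7% in the difference, or 11% in the second half, with the ratio almost intact. It becomes material only if withdrawal differs by arm. The assumed 25% v 10% costs about 15% of the difference (24% in the second half) and can lift type I error above 5%. All sizes rest on assumed recurrence risks, withdrawal unrelated to recurrence, and no observation after leaving.

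These are other efficacy endpoints outside the fixed sequence. Recurrence days are descriptive only.

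**What to change.** In SAP 7.4.4:

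1. Analyse the number of recurrences in FAS1 with a negative binomial model containing treatment, baseline IGA stratum, and log observed time in the interval as offset. For W9 to W16 each subject contributes the time observed in that interval. State the interval limits in study days.
2. Report recurrence days per unit of observed time.
3. Keep the number and percentage of subjects with recurrence as a descriptive table, with its denominator stated for each interval.
4. Add, as support, a Kaplan-Meier and IGA-stratified log-rank analysis of first recurrence. Note that it assumes non-informative withdrawal.

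Do not make a second-half analysis restricted to subjects still under observation the main one, because that conditions on a post-randomisation outcome. A subject with no time in W9 to W16 adds nothing to the rate model for that interval either, so the full Stage 1 interval should carry the weight.

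Cost: SAP wording and modest programming. Protocol 8.2.2 already has onset and duration recorded, so no new data are needed. The main estimate becomes a rate ratio, which is less direct to read than a percentage, and it too is unbiased only if withdrawal is unrelated to recurrence.
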